10. INTERVENTION

Theoretical foundations and intervention framework_The TRIUMPH intervention incorporates health behavior change techniques based on principles derived from cognitive and behavioral therapies and social

Protocol: Trial of Integrated Smoking Cessation, Exercise and Weight Management in SMI

cognitive theory.¹⁸⁶⁻¹⁸⁹ Participants are placed in groups based on readiness to quit smoking as assessed by the Transtheoretical Model.⁷³⁻⁷⁵ Motivational interviewing, a patient-centered and directive approach well suited to SMI, is used to enhance intrinsic motivation to stop smoking, increase exercise and improve diet.¹⁹⁰⁻¹⁹³ The intervention is designed to be positive, goal-oriented and focused on identifying and overcoming each individual's specific barriers to behavior change. Importantly, the intervention conceptualizes tobacco dependence and obesity as chronic conditions, which require skill building and ongoing strategies to achieve and maintain healthy behaviors, consistent with a psychiatric rehabilitation and recovery model.^{194,195}

Addressing weight and physical activity together with smoking cessation will exert a synergistic, positive effect on health outcomes. Working with participants to achieve healthy eating and exercise behaviors as a way to avoid weight gain may minimize this potential barrier to smoking cessation. Participating in group exercise can provide social support and serve as an alternate behavior to smoking. Moreover, exercise may alleviate some nicotine withdrawal symptoms (e.g., insomnia, negative affect) and have positive effects on abstinence. We also expect that smoking cessation will result in improved respiratory capacity and endurance, which will be evident during exercise sessions, and will provide positive, reinforcing feedback. We will base our examination of implementation issues on the RE-AIM framework¹⁸⁴.

Previous work has supported cognitive tailoring.^{26,27,51,52,69,125,196} The intervention will be tailored to meet the cognitive needs of SMI who often have memory and executive function impairment.^{197,198} Tailoring includes emphasized learning of specific skills repeatedly, breaking material into small units, using learning aides to reduce memory and attention requirements, and rehearsing behavioral skills.¹⁹⁹⁻²⁰¹ Materials emphasize message simplicity. Choices are limited to accommodate for decision-making deficits, e.g., coping strategies for smoking urges are distilled to the “4 Ds”—deep breathe, do something else, drink water or delay.

TRIUMPH Intervention goals focus on all 4 AHA CV health behaviors: smoking abstinence; healthy diet; healthy weight and regular physical activity.²⁰² The primary goal is smoking abstinence. Goals will be individualized weight goals based on baseline BMI (i.e., weight maintenance if normal BMI, weight loss if BMI ≥ 25) and provide intermediate weight, diet and exercise targets while maintaining a focus on smoking abstinence.

The TRIUMPH intervention is delivered separately from mental health or medical services the participants may already be receiving. The intervention is not a substitution for participants' ongoing mental health or medical care.

Protocol: Trial of Integrated Smoking Cessation, Exercise and Weight Management in SMI

Intervention Components (Table 3)

Table 3. TRIUMPH Intervention Overview: Integrated Smoking Cessation, Weight Management and Exercise			
Phase	Motivational Enhancement	Active Smoking Cessation	Relapse Prevention
Inclusion	Interested in quitting, not ready to set date within 30 days*	Willing to set a quit date within 30 days*	2 consecutive weeks of smoking abstinence
Length	4 weeks (may be repeated up to 2x)	7 weeks (may be repeated up to 2x)	Ongoing until end of study
Intervention Components			
Group Sessions	
 -60 minutes weekly with coach -Focused on increasing motivation to quit and weight management -CO and weight monitoring 	
 -60 minutes weekly with coach -Focused on setting and implementing quit date and weight management - Prior to the 1st smoking cessation group – prescriber to meet with participants to start medications (medications to start first week of group) -CO and weight monitoring 	
 -60 minutes weekly month 1 -biweekly month 2, then monthly -Focused on relapse prevention and weight management -CO and weight monitoring
Individual sessions	20-30 minutes bi-weekly for 3 months, then monthly to review individualized goals (smoking and weight management) and support behavior change.		
Pharmacotherapy	Education, and participants may start pharmacotherapy with Varenicline (+/- NRT) or Bupropion + NRT	Varenicline (+/- NRT) or Bupropion + NRT	Varenicline (+/- NRT) or Bupropion + NRT
Exercise	Group exercise class, 50 minutes, 2-3 x/week Outpatient Ppts: DVDs, pedometers, group exercise classes		
Text messaging	Participants enrolled in text messaging campaigns based on Intervention Track and whether they have experience with text messaging.		

*Participants start the study in one of these phases, tailored to their motivation to quit
			

Protocol: Trial of Integrated Smoking Cessation, Exercise and Weight Management in SMI

Table 4. TRIUMPH Intervention. Selected Examples of Strategies by Treatment Phase		
	Smoking Cessation Focus	Weight/Exercise Focus
Motivational Enhancement Phase		
Education	-Address knowledge deficits and correct misperceptions (e.g., fear of pharmacotherapy, “cold turkey” works)	-Address knowledge deficits and correct misperceptions about weight management (e.g., fear of weight gain after quitting)
Building success and motivation	-Build confidence by reducing smoking or making trial quit attempt; present peer models	-Discuss how experience of being more active in exercise class has influenced readiness to quit
Active Smoking Cessation Phase		
Self-monitoring	-Create awareness of smoking behavior -Identify smoking triggers -Track correspondence of CO with smoking behavior	-Create awareness of sugar sweetened beverage intake -Increase awareness of snacking habits and weight -Promote replacement behaviors like “get 200 steps not a smoke”
Coping with withdrawal and cravings	-Present coping strategies for withdrawal and craving	-Discuss low calorie, healthy choices to substitute for cigarettes (e.g., sugar-free lollipop or gum) -Discuss benefits of exercise on craving and depression
Preparing to quit	-Plan day of quit attempt including strategies to avoid triggers	-Plan what food to have available on quit attempt day. -Plan exercise schedule for week of quit date for less idle time.
Relapse Prevention Phase		
Coping with stress	-Broaden coping strategies for stress	-Advise crunchy fruit and vegetables not junk food when stressed -Exercise as a way to reduce stress.
Rewarding yourself	-Identify and implement rewards other than smoking	- Identify non food rewards for meeting goals -Focus on personal identified benefits of weight loss and fitness
All phases		
Social support	-Facilitate participation in a group with others who are working to attain similar goals -Supportive text messages	-Provide additional smoke free environments and activities (e.g., group exercise, gym) -Encourage support among group for healthier food choices

Integrated Smoking Cessation and Weight Management Group sessions. Participants will enter a group tailored for their readiness to set a smoking cessation date. Participants will move sequentially from one type of group to the next, from motivational enhancement to smoking cessation as they progress to being ready to quit within 30 days, and then to relapse prevention when they attain abstinence. Participants who do not progress may repeat group curricula as needed. We have previously used all the group curricular elements successfully. Drs. have found structured groups to be highly successful in contributing to attaining and maintaining smoking abstinence.^{26,27,51,52,67,69} Similarly, we have found groups to be powerful in creating a supportive environment for weight management and exercise in SMI.^{122,125} Groups will include time for individual weigh-ins and include instruction in using medications including NRT.

Motivational enhancement phase: Participants not ready to set quit date within 30 days at baseline enter this group. Content will focus on improving perception of feasibility and benefits of attempting to quit smoking. Videotaped interviews with previous patients will illustrate increased readiness to make a quit attempt among peer models. Care will be taken to understand specific concerns about quitting smoking (e.g., fear of weight gain, symptom exacerbation), to problem-solve barriers and envision each participant’s cessation strategy. We will educate participants about pharmacotherapy, and participants may initiate pharmacotherapy. We will encourage exercise as a strategy for improving readiness and ability to quit. The goal of this phase is to explore and resolve ambivalence regarding quitting, move to being ready to set a quit date within 30 days, and

Protocol: Trial of Integrated Smoking Cessation, Exercise and Weight Management in SMI

enter the 7-week active smoking cessation group. Those not ready will repeat the motivational enhancement group. If they are still not ready to set a quit date after the 2nd course, they will work with their coach in individual visits to explore barriers and reasons to quit with the goal of increasing motivation to join an active smoking cessation group.

Active smoking cessation phase includes participants expressing readiness to try to quit smoking within 30 days. The group will prepare for their quit date, set between weeks 4/5, and pharmacotherapy is initiated in this phase. Expired carbon monoxide (CO) will be measured weekly. Participants will self-monitor smoking triggers and develop plans for how to handle triggers after quitting. Skills training will enhance coping with urges to smoke, physical withdrawal, and psychiatric symptoms. (Tables 3/4,) Videos of peers and peer guest speakers will be included to increase self-efficacy through identification with a successful peer model. Smoking issues specific to those with SMI will be discussed. Eating, exercise and weight management strategies will be incorporated throughout, paralleling smoking-related content. This group may be repeated.

Relapse prevention phase. Participants join this phase when they achieve ≥14 days biochemically confirmed continuous abstinence at the end of the 7-week smoking cessation phase. Sessions focus on learning and applying key cognitive and behavioral skills to high-risk situations, including refusal skills, problem-solving, identifying and responding to permission-giving beliefs, and developing and implementing personalized relapse prevention plans. Weight management strategies for high-risk situations and problem solving will be integrated throughout. (Tables 3, 4). Those who slip or resume smoking will be asked to remain in the group with the goal of regaining abstinence through subsequent supported quit attempts.

Individual sessions with the health coach will focus on reviewing progress and problem solving to enhance participants' strategies for smoking cessation and weight management. The coach will review relevant process data tailored to individuals' needs (e.g., expired CO, study session participation, gym use, use of texting, medication adherence, expired CO, weight, and step counts), and using motivational interviewing, will provide feedback and address readiness to adopt further changes. The potential synergistic effects of efforts to achieve goals across more than one type of health behavior will be discussed and reinforced as appropriate. Additional sessions may be scheduled for those not ready to set a quit date after 2 cycles of the 4-week motivational enhancement program or for those who do not achieve 2-week abstinence after 2 7-week active smoking cessation cycles. These participants will continue to participate in all other aspects of the intervention, and will be reassessed and encouraged to rejoin the appropriate group when ready.

Pharmacotherapy for smoking cessation in SMI is universally recommended, but infrequently used in most settings.^{12,72} The study physician(s) are trained education on use, risks, benefits and monitoring of pharmacotherapeutic cessation aids in SMI, and will prescribe and monitor medications for intervention participants, coordinating with and supported by others on the study team. These psychiatrists will discuss medication choice with participants and take their preferences into account while assessing clinical appropriateness for varenicline+/-NRT, and bupropion+NRT (patches with lozenges/gum) Varenicline has been associated with higher abstinence,^{67,203,204} so we expect it will be used preferentially. We will use standard dosing for varenicline and bupropion. Varenicline dosing is 0.5mg for 3 days, 0.5 mg bid for 4 days and then 1mg bid. Subsequent prescriptions are 1mg po bid. Varenicline will be provided by Pfizer. Bupropion is 150mg pod bid SR formulation. Those with adverse effects with varenicline limiting tolerability will be offered a lower dose, or bupropion+NRT. Bupropion+NRT will be offered to those with varenicline contraindications, and vice versa. Once initiated, the goal will be for participants to use medication for the study duration for sustained abstinence, however, if needed they may stop and then resume medication or switch therapies. This flexible approach should improve cessation rates. Physician study visits for smoking cessation pharmacotherapy are separate from the participants' regular mental health visits. Participants will continue to see their regular psychiatrist for mental health care. The physicians prescribing smoking cessation pharmacotherapy will be study team members and will communicate with the participants' regular psychiatrists about the intervention, but will not deliver regular mental health care.

Exercise program. Three approaches will enable participants to achieve 150 mins/week of moderate intensity

Protocol: Trial of Integrated Smoking Cessation, Exercise and Weight Management in SMI

physical activity.²⁰⁵ First, group exercise classes will be held two to three times a week at mental health programs. Under supervision of the intervention director, exercise leaders will deliver classes following a progression appropriate for sedentary adults and designed to build exercise confidence.²⁰⁶ Second, participants will be provided access to a local gym (e.g., at Bayview, or City of Gaithersburg's Bohrer Park gym facilities). Participants will be provided with 3 orientation sessions teaching them to use the aerobic fitness equipment (e.g., treadmills, stationary bicycles). Third, we will use text messaging prompts and pedometers to encourage participants to achieve a 10,000 steps per day goal²⁰⁷. Exercise instruction will be adapted to the heterogeneity of this population including psychiatric symptoms, motor control challenges and cognitive levels.^{121,122,124,125} During individual sessions, coaches will help participants develop individualized physical activity goals and strategies to overcome related barriers (e.g., preparation for class, places to walk). Exercise videos will be distributed.

Text messaging support. Texts will provide reminders to use behavioral strategies introduced in group and individual sessions, will encourage self-monitoring (e.g., weight, pedometer steps, number of cigarettes) and provide positive feedback for attainment of targeted goals, tailored to the participant's intervention phase. For example, in motivational enhancement, messages will focus on personal benefits of abstinence and preparing for a trial quit date; in active smoking cessation, texts will count down to the quit date and remind participants to use pharmacotherapy. Eating and exercise messages will parallel and integrate with smoking-related content (Table 4) (e.g., choosing healthy foods and exercise to cope with stress). Responses are captured in a database enabling the coach to track and review participant progress, thereby creating accountability and connection to the coach between intervention sessions. Participants will be provided cell phones and/or offered a prepaid phone card if they do not have phones/unlimited texting, allowing for connection to the platform and to other participants. Participants will be oriented to the texting platform. Smoking messages will be based on NCI's Quitnowtxt.²⁰⁸ Text messaging support will be piloted and interviews will be conducted with smokers with SMI to assure ease of use, acceptability and satisfaction with the technology.

Self-monitoring: Participants will be encouraged to track eating, weight, exercise and smoking behaviors appropriate for their individually tailored behavioral goals and cognitive abilities using texting, and paper trackers if needed. Coaches review data with participants at individual sessions and with the intervention team in case management.

Reinforcements: Contingency management reduces smoking in those with SMI and has been used by the team.^{209-211 148,149} and for attending 2 exercise groups/ week. Reinforcement plans are small incentives for group and individual session attendance and for low smokelyzer or cotinine readings. These will consist of earning points that may be traded in for small gifts, or earning up to \$3 for session attendance or biochemically confirmed smoking abstinence with low smokelyzer reading or cotinine value.

Peer mentor guest speakers. In addition to the videotaped peer presentations, trained peer mentors from [name] smoking cessation studies will be invited as guest role models in selected group sessions to provide encouragement and increase self-efficacy for smoking cessation. They are trained and will provide short testimonials focused on their experience of mental illness, smoking history and successful abstinence.

Health coaches leading the integrated sessions will be community mental health program employees. Embedding coaches at sites will enable optimal coordination of intervention implementation and allow them the opportunity to take advantage of everyday encounters, in addition to scheduled sessions, to reinforce healthy choices and behavior change (e.g., encouraging exercise participation). Coaches will have a background in mental health and/or health behavior change with a skill level typical for a community health educator, and will not require a Master's degree.²¹² The coach is modeled after a position that would be feasible and sustainable in a community mental health setting. Coaches will receive training in all aspects of the TRIUMPH intervention and have supervision and ongoing interaction the Intervention Director and investigators.^{213,214}

Training, case management and quality control: High-quality intervention delivery will be assured by providing initial and ongoing training of manualized approaches to smoking, weight management and exercise. Coaches

Protocol: Trial of Integrated Smoking Cessation, Exercise and Weight Management in SMI

will receive intensive baseline training in motivational interviewing, group facilitation and conducting individual sessions for health behavior change in SMI and will attend Tobacco Treatment Specialist training.²¹⁵ They will follow Leaders' Guides and session outlines; exercise leaders will follow a standard protocol. Case management will be provided through regular meetings between coaches and supervisors. Quality control will be assured through reviewing a sample of group and individual sessions, taped or observed in person, rated for fidelity. Feedback will be shared with coaches.

11. CONTROL GROUP

Those assigned to the control group will receive usual care and will also receive referral to a telephone smoking quit line, a list of exercise resources and the NHLBI brochure Aim for a Healthy Weight. They will also receive a quarterly health newsletter.

12. DATA MANAGEMENT

We will store data in REDCap.²¹⁶ Built-in range and logic checks will prompt data checks and confirmation in real-time during data collection. The analyst will routinely conduct thorough checking and cleaning, examining distributions and data patterns and evaluation to detect inconsistencies. Outliers (e.g., extreme weight changes) will be identified using Rosner's extreme Studentized deviate (ESD).²¹⁷ Every effort will be made to determine correctness of outliers in a timely manner. Confirmed outliers will be flagged and set aside in the principal secondary analyses. Those removed will be treated as all other missing data; sensitivity analyses will be conducted to assess influence of outliers on results. The analyst will create detailed variable documentation and conduct analysis per protocol under direction of [name], statistician.

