13. DATA ANALYSIS

Primary Outcome: The primary outcome will be 7-day point prevalence smoking abstinence at 18 months, defined as self-report of 7 days of not smoking, confirmed by expired CO <8ppm with a Bedfont Smokerlyzer II.^{148,153,218 182} Biochemical verification with available urine cotinine (if not on NRT) and/or anabasine will be used as needed to verify self-reported abstinence, particularly if the validity of CO is expected to be low (e.g. COPD or difficulty forming an adequate seal on the smokerlyzer); and if CO is greater than 8 as this could be from second hand smoke or smoked cannabis.¹⁴⁸⁻¹⁵⁰

7-day smoking abstinence at 6,12 and 15 mo. are secondary outcomes.

Other Secondary outcomes focus on AHA metrics for health risk behaviors²⁰² and include: a) continuous abstinence with 1) % continually abstinent over 3 mo. (based on self-reports of abstinence since last visit, using timeline follow-back²¹⁹, and biochemical verification at 15 and 18 month visits), 2) total days abstinent in the study with the same method, b) Weight and BMI; c) Physical fitness with 6-minute walk;¹⁵⁴⁻¹⁵⁶ and d) Healthy diet.¹⁶⁰ We will assess 10-year probability of a CVD event with the global Framingham Risk Score (FRS) incorporating smoking, total and HDL-cholesterol, systolic blood pressure and diabetes mellitus.²²⁰ Others include: health status (SF-12)¹⁶²; Quality of life (Euroqol);¹⁶³⁻¹⁶⁵ psychiatric symptoms (BPRS);¹⁷⁰ ED use and hospitalizations.

We will also examine the difference of mean CO change over time between intervention arms, and, among continuing cigarette smokers, change of mean number of cigarettes smoked per day over time between intervention arms.

For the primary outcome, we will also perform sensitivity analyses using expired CO<6ppm for abstinent confirmation, as this cutpoint has become more acceptable during the time the trial has been implemented.¹⁵⁰ The outcome using this alternative definition will be modeled in the same fashion.

Our recruitment goal is 220 participants will be recruited from 2 community mental health organizations, enrolled, and randomized in equal allocation to active intervention (Group B) and control (Group A), stratified

Protocol: Trial of Integrated Smoking Cessation, Exercise and Weight Management in SMI

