Although model (1) will support our principal analyses, there is an attractive, transition model alternative. A first-order, autoregressive transition model is a useful adjunct to (1). Note for each participant the outcome is a binary time series that can be analyzed via a series of linked, 2×2 tables (rows are values at visit $(j-1)$, columns at visit j , where visit 0 is baseline), with transitions modeled by logistic regression with treatment effects and, if desired, other covariates. This model could be used to characterize probability of successful abstinence at 12-months among those who were still smokers at 6-months, and at 18-months among those who were smokers at 12-months. Similarly we could estimate relapse rate at a given visit among quitters at the previous visit.

Missing data: Based on our experience, we anticipate less than 10% of follow-up data will be missing.¹²⁵ Prevention is far superior to statistical treatments; every effort will be made to collect data on all randomized. We will use two approaches to missing data. First, in smoking cessation trials, conventionally, those missing smoking data are assumed to be smoking, and we will use this method to be comparable to the field.

^{203,204,222,223} Second, we will perform analyses on the assumption that data is missing at random (MAR). The underlying missing data process determines the biasing effects of missing data and structures valid analytic strategies.²²⁴ If the probability of a potential observation being missing depends on what has, but not on what has not been observed, termed MAR, then estimates based on an appropriate analytic model (both the mean and error structure) for the observed data will not be biased. A valid model for the observed data allows the missing data process to be ignored. If missing is informative, meaning that the probability of an observation being missing depends on the value of that observation after accounting for all the observed data, then bias cannot be avoided by modeling the observed data alone, and the impact should be evaluated using sensitivity analysis. Given that MAR is not a testable hypothesis, we will perform sensitivity analyses to evaluate the robustness of MAR results with multiple imputation using a model derived from our analytical model under MAR, maintaining the covariance structure and modifying the imputation mean according to informative missing data scenarios.

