Secondary Analyses (Secondary Aims 1-2): The odds ratio of maintaining continuous abstinence over 15 to 18 months months will be modeled using logistic regression. To evaluate between group difference in change for secondary continuous outcomes such as continuous smoking abstinence (number of days abstinent), weight, 6-minute walk test, global FRS, and psychiatric symptoms (BPRS), we will use linear mixed models employing visit by intervention interaction terms in the mean model and unstructured correlation in the covariance model to estimate intervention effects over time. Outcomes will be log-transformed as appropriate. Emergency department visits and hospitalizations over the three 6-month periods (0-6, 6-12, 12-18 months) will be modeled using mixed effect Poisson regression. All these analyses will be conducted under intention to treat principles. Covariates such as study site and set quit date indicators and other variables associated with

Protocol: Trial of Integrated Smoking Cessation, Exercise and Weight Management in SMI

presence of missing data will be included in the mean model as appropriate.

We will also explore the difference of mean CO change over time between intervention arms, and, among continuing cigarette smokers, change of mean number of cigarettes smoked per day over time between intervention arms using mixed effects regression modeling approach in a similar fashion. For the first exploratory analysis, we will use all patients in the analysis. In the second analysis, we will determine if patients who continue to smoke, smoke less. In this analysis, we will include only patients who are not abstinent. We will use the pattern mixture approach by examining patients in separate groups according to their pattern of missing data to better understand the probability of missing based on patterns of the observed data to inform proper modeling and sensitivity analyses addressing potential informative missing mechanism.

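### Section 12 sets undefined *confirmed* outliers aside in the principal secondary analyses; if these are verified values, genuine data are dropped for their size, with bias of undeterminable size and direction

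*Combined protocol and SAP*

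**What the plan says.** Section 12 describes a sequence. Outliers, with extreme weight changes as the only example, are identified by Rosner's extreme Studentized deviate (ESD). Then: "Every effort will be made to determine correctness of outliers in a timely manner". Then: "Confirmed outliers will be flagged and set aside in the principal secondary analyses. Those removed will be treated as all other missing data". The same sentence ends with a safeguard: "sensitivity analyses will be conducted to assess influence of outliers on results".

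Section 13 (Secondary Analyses) fits linear mixed models with visit-by-intervention terms to "secondary continuous outcomes such as continuous smoking abstinence (number of days abstinent), weight, 6-minute walk test, global FRS, and psychiatric symptoms (BPRS"). It adds "Outcomes will be log-transformed as appropriate" and "All these analyses will be conducted under intention to treat principles". Under Missing data, the same section calls missingness informative when "the probability of an observation being missing depends on the value of that observation after accounting for all the observed data", and says that modelling the observed data alone cannot then avoid bias.

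The plan does not say what *confirmed* means. It also gives no ESD significance level, no maximum number of removals, no choice between pooled and by-arm use, and no order relative to any log transformation.

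**The concern.** ESD selects values by their distance from the mean. A correctness check can then end in two ways: the value is wrong, or it is right. Removing wrong values is ordinary cleaning. Removing right ones makes missingness depend on the value itself, yet the plan treats those gaps like any others.

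Two features favour the second reading. The word follows directly on a check of correctness. And an analysis of how outliers influence the results has little purpose if they are known errors.

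At stake are the principal estimates for the continuous secondary outcomes. Where genuine extremes fall mostly in one arm, the between-arm difference shifts, and the deleted-data result remains the headline one.

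**Working it through.** **1. SD for weight change.** The precision paragraph in Section 13 gives a half-width of 1.96 × √(2/n) × SD and quotes 5.0 lb for weight. No SD is stated, so the figure can be inverted but not independently reproduced. With n = 110 per arm (220 allocated equally): SD = 5.0 / (1.96 × √(2/110)) = 5.0 / 0.2643 = 18.9 lb.

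**2. How far out a value must lie.** Assume an ESD alpha of 0.05. The first critical value is 3.634 for n = 220 pooled and 3.416 for n = 110 by arm. Multiplied by 18.9 lb, these are about 69 lb and 65 lb from the mean.

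**3. Weight, single visit.** Assumptions: normal changes with SD 18.9 lb, control mean 0, each active participant extreme with probability 5%, pooled ESD, at most 10 removals. The shift is the estimate after ESD minus the estimate with all values.

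| Extreme 5% of active arm | Rest of active arm | True difference | Shift |
|---|---|---|---|
| lose 7 or 20 lb | lose 2 lb | −2.25 or −2.9 lb | about 0 |
| lose 30 lb | lose 2 lb | −3.4 lb | 0.05 lb toward null |
| lose 50 lb | lose 2 lb | −4.4 lb | 0.3 lb toward null |
| lose 70 lb | lose 2 lb | −5.4 lb | 1.5 lb toward null |
| lose 80 lb | lose 2 lb | −5.9 lb | 2.6 lb toward null |
| gain 50 lb | lose 7 lb | −4.15 lb | about 0.5 lb away from null |
| gain 70 lb | lose 7 lb | −3.15 lb | about 1.9 lb away from null |

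The true difference is 0.05 × extreme + 0.95 × rest; for the last row, 3.5 − 6.65 = −3.15. In that row the estimate moves from about −3.1 to −5.0 lb. The 7-lb loss is the earlier weight-loss trial's result quoted in Section 3.

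**4. Weight, planned mixed model.** Four follow-up visits, assumed correlation 0.6–0.8, extreme losses in the active arm only. The shift falls to 0.1–0.2 lb at 50 lb (95% interval coverage 94–96%) and 0.7–1.0 lb at 70 lb (coverage 92–94%).

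**5. Days abstinent.** Section 12 neither names nor exempts this outcome, so applying the rule here is an inference. Section 13 defines it as "total days abstinent in the study with the same method", taken here as one value per participant. Assume 19% against 5% abstainers (rates from Table 5), abstainers' days uniform on 90–540 (mean 315), and others exponential with mean 10. The true difference is (0.19 − 0.05) × (315 − 10) = 42.7 days.

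- Raw scale, pooled ESD: at most 1, 5, 10 or 20 removals give about 40, 31, 21 or 6.5 days. The cap is reached in 96–100% of runs, so the unstated cap sets the answer, and the values removed are largely those of successful quitters.
- Raw scale, by arm: caps of 1 or 3 give about 45 days, slightly away from the null; a cap of 20 gives about 4.
- After log(1 + days), pooled, at most 10 removals: 0–0.1 values removed and no material change in five of six assumed cases. If every non-abstainer has exactly zero days, about 5 values go and the log difference falls from 0.79 to 0.63.

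No figure was computed for the 6-minute walk, Framingham score or BPRS.

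**The case against.** The strongest reply is that this is an undefined word, not a demonstrated deletion of valid data. The rule sits among range and logic checks, and Sections 8 and 14 provide for queries and for correction against source documents, so *confirmed* may mean confirmed as wrong. That stands as a possibility, and on that reading there is no bias to discuss. Section 14 can also be argued the other way: errors found at source are corrected, which leaves mainly genuine extremes to set aside.

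Second, safeguards exist. Outlier sensitivity analyses are promised, and treating removed values as missing arguably brings in the informative-missingness scenarios of Section 13. These would reveal a difference. They would not change which result is principal, and the content of the outlier analyses is not specified.

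Third, trimming can help. With symmetric heavy tails (t with 4 df, true difference −5 lb), pooled ESD removes about 2 values, moves the estimate only from −4.9 to −4.8 lb, cuts the standard error from 2.52 to 2.26 lb and raises power from 0.49 to 0.55. This is correct, but it depends on the tails being symmetric across arms.

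A reader might infer more than the documents support:

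- *That the bias runs toward no effect.* The gain rows in the table show the opposite. Sections 3 and 16 describe weight gain after quitting, and more quitters are expected in the active arm.
- *That intention to treat is breached.* Setting aside one visit's value does not remove a participant or change the assigned arm. The fit is awkward, but it is not a contradiction.
- *That the days-abstinent result would be destroyed.* The large figures need raw-scale ESD, assumed distributions and many removals, although Section 13 allows log transformation.

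**Conclusion.** The point holds conditionally. If *confirmed* means verified values, the principal secondary analyses delete genuine data for their size and then treat the gaps as ordinary missing data, contrary to the plan's own account of informative missingness. If it means documented errors, the rule is sound and needs only a definition.

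The bias depends on which arm holds the extremes and on their sign. Its size cannot be determined from the documents, because the SD, the frequency of extremes and every ESD setting are absent. For weight it is negligible at ordinary changes; the shifts of 1.5 lb and more, against a stated precision of 5.0 lb, need mean changes of 70 lb or more in a subgroup, which nothing in the documents leads one to expect. The days-abstinent figures are illustrative only: they show that the unstated scale and cap could matter, not that they will. The binary primary outcome is unaffected. Severity: minor.

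**What to change.** In Section 12, define *confirmed* and reverse the roles of the two analyses:

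- Correct, or set to missing, only values documented as erroneous, with the review done blind to arm.
- Keep all verified values in the principal secondary analyses.
- Make the ESD-excluded analysis the sensitivity analysis, and state its alpha, maximum number of removals, pooled or by-arm use, and scale (before or after any log transformation).

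This takes one or two sentences and no new data, since analyses with and without the outliers are in effect already planned. The cost is slightly wider intervals when genuine extremes occur.
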